2. Feasibility of recruitment, enrollment, retention and adherence with a two-arm pilot RCT (WhatsApp and control). A target retention rate of at least 90% completing the pilot trial is sought. Retention will be measured by the proportion of participants who will remain in the study by the end of the follow-up period. If we are unable to achieve this target, alternative strategies will be considered for the UH3 phase. One of the primary objectives is to estimate the proportion of successful return blood donation for planning the programmatic randomized clinical trial in the UH3 phase.
3. Acceptability will be assessed with quantitative surveys and participant focus groups to understand the opinions and perspectives of acceptability, effectiveness, feasibility and cultural appropriateness of the docu-drama, WhatsApp and control communication interventions.

Secondary Objectives

To design culturally appropriate communication interventions: docu-drama and WhatsApp groups for retaining first-time blood donors using the PRECEDE-PROCEED framework.

To examine intervention-specific increases in knowledge, attitudes, beliefs, motivations, intention, and relatedness as potential mediators of intention to donate among first-time blood donors. Evaluate the reliability of new or modified outcome measurement instruments.

Study Design

The pilot study utilizes a mixed-methods approach to develop a novel docu-drama communication strategy, evaluate the feasibility of a larger pragmatic randomized controlled trial (RCT) of a WhatsApp based communication strategy and assess acceptability of the communication strategy aimed to increase blood donation among first time blood donors within the catchment areas of the SZBC.

There are two communication interventions: docu-drama and WhatsApp. However, because the development of the docu-drama takes more time, it will not be feasible to include the docu-drama intervention in the pilot RCT, recruit 100% participants, follow up for 6-months for the primary outcome and evaluate the secondary outcomes, considering the duration the UG3 phase. Therefore, only the WhatsApp intervention will be piloted in the RCT. The docu-drama intervention will be designed and test-run in preparation for an RCT in the UH3 phase.

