The participants will be invited to participate in screening after blood donation at SZBC sites.

Table 1: Schedule of assessments for pilot RCT

Assessment	Screening (At first-time donation)	Baseline A pre- randomization (Day 0)	Baseline B post- randomization (Day 0)	6-month follow-up (Days 176- 190) ¹	6-12 months follow-up
Informed Consent Form	X				
Demographics	X				
Blood donation attitudes, subjective norms, perceived behavioural control, and intention		X		X	
Randomization			X		
Intention of using the intervention			X		
Acceptability of the intervention			X	X	
Feasibility of the intervention			X	X	
Cultural appropriateness of the intervention			X	X	
Perceived usefulness of the intervention			X	X	
Perceived ease of use of the intervention			X	X	
Intervention relatedness			X	X	
Return blood donation attempts ²				X	
Focus groups of participant views of acceptability, effectiveness, feasibility, and cultural appropriateness					X
Note: The participants involved in the test-run of the docu-drama will be surveyed prior-to and after the docu-drama with all instruments (except blood donation attempts) and participate in facilitator-led focus groups.					
¹ 6-months with a 2-week window.					
² Donor return will be assessed via telephone calls and cross-checked with SZBC donor records.					

Follow-up assessments for the pilot RCT

There will be two follow-up assessments.

6 months

The 6-month assessment for the pilot RCT will occur over the phone with a 2-week window of the 6-month pilot. Donor return will be assessed via telephone calls and cross-checked with SZBC donor records. The six-month follow-up will repeat baseline post-randomization questionnaires and include the intention of using the intervention, acceptability of the intervention, feasibility of the intervention, cultural appropriateness of the intervention, perceived ease of use of the intervention, perceived usefulness of the intervention, and intervention relatedness. In line with definitions of acceptability, appropriateness and feasibility given by Weiner et al. (2017), we defined these characteristics as follows:

Acceptability is the perception among first-time blood donors that an intervention is agreeable or satisfactory for promoting blood donation. Thus, acceptability will be measured with a five-item questionnaire.

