Cultural appropriateness is the perceived fit, relevance, or compatibility of an intervention; and/or perceived fit of these interventions for promoting blood donation among first-time blood donors (Weiner et al., 2017). Cultural appropriateness will be measured with a five-item questionnaire.

Feasibility is defined as the extent to which an intervention, can be successfully used by the NBSG to promote blood donation among first-time blood donors. Feasibility will be measured with a six-item questionnaire by integrating appropriateness measures (Weiner et al., 2017) and the role of culture as it pertains to health communication (Kreuter & McClure, 2004).

The extent to which respondents participated in the activities will also be documented for the WhatsApp intervention and includes not leaving the WhatsApp group during the intervention; evidence of having read a post, an indicator that can be used in closed WhatsApp groups such as the one to be implemented in the study, and posting at least once a month. Those not reading 50% of the weekly post by the moderator and not posting at least three times during the intervention will be considered as non-adherent. The WhatsApp group moderator will obtain participation data by checking the read status and post by participants.

6–12 months

The second follow-up will involve facilitator-led participant focus group (8 participants per group) discussions of views on acceptability, effectiveness, feasibility, and cultural appropriateness.

The participants involved in the test-run of the docu-drama will be surveyed after the docu-drama with all follow-up instruments (except blood donation attempts) and participate in facilitator-led focus-groups similar to participants in the pilot RCT.

All the constructs will be constructed using a 5-point Likert scale ranging from “completely disagree” to “completely agree”. Focus group discussions will also be held with 6–8 participants from each group to assess all the above implementation research outcomes of interventions.

Risk/Benefit Assessment

Known Potential Risks

Potential risks may include breach of confidentiality and any discomfort that may result from discussions of the docu-drama or issues about blood donation. However, these risks are minimal and are not more than those encountered in everyday life.

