- Ask the respondent if they feel the message said anything that might upset or offend people (if the answer is yes, probe to get what is offensive or upsetting).
- Ask the respondents what they think this message is asking them to do (probe their willingness to follow the message).
- Ask the respondent(s) what they liked most about the message.
- Ask the respondent(s) what would encourage them to follow the message they have just heard (probe if there is something that would discourage them).
- Ask the respondents to whom they think this message is directed?
- Ask if docu-drama says or suggests that they must do something? If yes, what?
- Ask if they would be willing to follow the advice given? Why/Why not?
- Ask the respondent(s) if the message is appropriate for blood donors
- Ask the respondent(s) if there is anything in the message which they would say differently (ask them to say it if applicable).
- How would you gauge the quality of the docu-drama program in terms of sound (volume) and words spoken?
- Ask the respondent(s) whether the sound level (volume) acceptable
- Ask the respondent(s) how they would rate the duration of the docu-drama (probe if too long, too short or just right).

- q. Ask respondents questions that could be asked of the audience to spark discussions and why
- r. Ask the respondents if they have any further questions/observations.

Docu-drama – acceptability, feasibility, cultural appropriateness

You watched docu-drama on blood donation and participated in the discussion. We would like to seek your feedback on it.

- a. To what extent was the use of docu-drama and its discussion for sharing your experience with blood donation acceptable to you?
- b. To what extent was the use of docu-drama and its discussion for sharing your experience with blood donation culturally appropriate (for example, language for the drama and discussion, religious beliefs or differences, concept in line with your personal experiences), for you?
- c. To what extent was the use of docu-drama and its discussion for sharing your experience with blood donation effective?
- d. How did the use of docu-drama influence your knowledge about blood donation?
- e. How did the use of docu-drama influence your beliefs about blood donation?
- f. How did the use of docu-drama influence your intention to return to give blood?
- g. Indicate the elements of the docu-drama intervention you preferred and why
 - i. Watching the docu-drama

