- a. You have been invited here to offer your views and opinions.
- b. Again, there are no right or wrong answers and it's okay to be critical. I want to hear your views and opinions about whether you like or dislike something you see or hear.
- c. There will be observers.
- d. You may excuse yourself from the conversation at any time for any reason.
- e. Although this session will be audio taped, it will remain confidential and will ONLY be used to capture everything that is being said today, for the purpose of listening to it again to get the message well. Please feel free to say exactly what is on your mind as nothing will be attributed to any particular person in our report.
- f. Lastly, please turn off the ringers on your cell phones.

ADDITIONAL GUIDELINES

- a. Everyone's participation is important.
- b. Please speak one at a time and avoid side conversations.
- c. Please use any of your names that you are comfortable with only during the discussion.
- d. Respect each other's opinions.

Demographics:

- What is your name?
- How old are you?

WhatsApp

You have been in this WhatsApp group for the past six months. We will like seek your feedback in terms of the acceptability and feasibility of using WhatsApp to encourage blood donation.

- a. To what extent was the use of WhatsApp for sharing your experience with blood donation acceptable to you?
- b. To what extent was the use of WhatsApp for sharing your experience with blood donation culturally appropriate (for example, language for the drama and discussion, religious beliefs or differences, concept in line with your personal experiences) for you?
- c. To what extent was the use of WhatsApp for sharing your experience with blood donation effective?
- d. How did the use of WhatsApp influence your knowledge about blood donation?
- e. How did the use of WhatsApp influence your beliefs about blood donation?
- f. How did the use of WhatsApp influence your intention to return to give blood?
- g. Indicate the elements of the WhatsApp intervention you preferred and why
 - i Share moments of blood donation
 - ii Send blood donation images or videos
 - iii Send blood donation audio notes
 - iv Send blood donation motivational messages
 - v Comment on other posts
 - vi Send positive experiences with blood donation
 - vii Send negative experiences with blood donation?
- h. How frequently did you read messages or other information posted to the WhatsApp group and why?

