 - i. What prevented you from participating actively in the WhatsApp group on blood donation?
 - j. How can these barriers be resolved?
- k. What should be done to make the WhatsApp group on blood donation more acceptable to you?
- l. What should be done to make the WhatsApp group on blood donation more feasible for positively influencing first-time blood donor's attempt to give blood again?

6. Case Report Form for participants attending baseline visit

Baseline A

Participant ID:

Form Date:
(example: 01-APR-2021)

			2	0	2
Day	Month				Year

Bloodsafe Logo
Placeholder

Participant
3-letter code:

Site:

--	--

01 Korle-Bu Bld Bank
02 Korle-Bu Maternity
03 Pentecost Hospital
04 LEKMA Hospital
05 Maamobi Polyclinic
06 Accra Shopping Mall
07 Mobile Unit

Complete this form for all participants attending the C-CAD baseline visit.

A. Blood Donation

1. Who did the participant donate blood for?

- 1 A friend/acquaintance/colleague
- 2 A relative
- 3 The blood bank/Blood Service
- 4 The community
- 5 Other; specify: _____
- 6 No one in particular

B. Knowledge

What follows are a number of statements related to the participant's knowledge about donating blood.
Read each statement to the participant and have them indicate True or False.

	True	False
1. I need a special invitation to donate blood.	1 	0 
2. All people with diabetes or hypertension can donate blood.	1 	0 
3. A menstruating woman can donate blood.	1 	0 
4. 'Skinny' people can donate blood.	1 	0 
5. Breastfeeding women can donate blood.	1 	0 
6. People with HIV/AIDS can donate blood.	1 	0 
7. A person with a fever on the day of donation can still donate blood.	1 	0 
8. A person with low blood level can donate blood.	1 	0 
9. A man will not become impotent for donating blood.	1 	0 
10. I can donate blood at any donation site that I choose.	1 	0 
11. My blood can only be given to my family member or friend.	1 	0 

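### Items a–c of both focus-group guides rate the interventions as a means of sharing experience rather than of promoting donation, and neither guide asks directly whether they were feasible

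*Combined protocol and SAP*

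**What the plan says.** Primary objective 3 relies on surveys and on "participant focus groups to understand the opinions and perspectives of acceptability, effectiveness, feasibility and cultural appropriateness of the docu-drama, WhatsApp and control communication interventions". The Qualitative Data Analysis section likewise gives the focus groups the task of assessing acceptability, feasibility and cultural appropriateness.

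The 6-month part of *Follow-up assessments for the pilot RCT* defines three of these four constructs. "Acceptability is the perception among first-time blood donors that an intervention is agreeable or satisfactory for promoting blood donation". Cultural appropriateness includes the "perceived fit of these interventions for promoting blood donation among first-time blood donors". Feasibility is whether the national blood service can successfully use the intervention for the same purpose. Effectiveness has no definition there. The Baseline B and Month 6 case report forms ask about acceptability, feasibility and cultural appropriateness with promotion of donation among first-time donors as the object.

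The guides take a different object. Tool 5, item c: "To what extent was the use of WhatsApp for sharing your experience with blood donation effective". Tool 3, evaluation block, item c: "To what extent was the use of docu-drama and its discussion for sharing your experience with blood donation effective". Items a and b in each guide use the same stem for acceptability and cultural appropriateness. Feasibility is named once in each guide as a request for improvements; tool 5, item l begins "What should be done to make the WhatsApp group on blood donation more feasible" and tool 3, item j is its counterpart. Item b of the WhatsApp guide illustrates cultural appropriateness with "language for the drama and discussion, religious beliefs or differences".

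**The concern.** The focus groups and the survey are meant to inform the same objective. If the survey asks whether WhatsApp is acceptable for promoting donation and the focus group asks whether it was acceptable for sharing experience, the two sets of results carry the same labels but refer to different things. A donor could truthfully say that the group worked well for exchanging experiences and still think it would bring nobody back.

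Sharing is also only part of what participants receive. In *Study Interventions*, the WhatsApp arm first gets weekly messages written by communication specialists and is then encouraged to discuss. A participant who read every message and never posted is asked in items a–c to rate something they did not do. Item g of tool 5 lists seven elements, all forms of sharing, sending or commenting; reading is touched only by item h.

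The stakes are highest for the docu-drama. It is not in the pilot RCT, and its only planned evaluation before the larger trial is a test run with 10 donors, so there is little chance to ask again.

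**Working it through.** No rate, power or sample-size figure enters this point. The check is a comparison of wording and a count of items.

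**Object of each construct**

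| Construct | Protocol definition | Case report forms | Guides (tools 3 and 5) |
|---|---|---|---|
| Acceptability | promoting donation | promoting donation | item a: sharing experience |
| Cultural appropriateness | promoting donation | promoting donation | item b: sharing experience |
| Effectiveness | none given | no scale of that name | item c: sharing experience |
| Feasibility | use by the blood service to promote donation | promoting donation | no rating item; improvement item only (tool 3 j, tool 5 l) |

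The guides therefore depart from a stated definition for acceptability and cultural appropriateness. For effectiveness there is no definition to depart from; the gap is that the plan never says what *effective* refers to.

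**Item counts**

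- Tool 5, WhatsApp block: items a–l, 12 in all. Sharing stem: a, b, c = 3 (3/12 = 25%). Direct feasibility rating: 0. Feasibility as an improvement request: 1 (l). Items that refer to giving blood again: 2 (f, l).
- Tool 3, evaluation block: items a–j, 10 in all. Sharing stem: a, b, c = 3 (3/10 = 30%). Direct feasibility rating: 0. Feasibility as an improvement request: 1 (j). Items that refer to giving blood again: 2 (f, j).
- Tool 3 also has an earlier message block that ends at item r, which makes 18 items, none with the sharing stem. Over the whole guide the share is 3/(18 + 10) = 3/28, or 11%.

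These three are the only questions in each guide that ask for a to-what-extent judgement, so the affected items are few but are the ones closest to the named constructs.

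**What other items recover**

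- Effectiveness: items d–f in both guides ask about influence on knowledge, beliefs and intention to return.
- Acceptability: tool 5, item k asks how to make the group more acceptable, without the sharing stem.
- Cultural appropriateness: tool 3's message block asks whether the message suits blood donors and whether it might offend. Tool 5 has no counterpart.
- Feasibility: both guides ask what prevented participation and how to resolve it, and items j and l tie feasibility to another attempt to donate.

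**Carry-over in tool 5.** The guide opens under a heading for the docu-drama group, although its only question block is for WhatsApp. The parenthetical example in item b is the same as in tool 3 and speaks of a drama that the WhatsApp arm is not shown.

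**The case against.** Sharing is not a side topic. The theory-of-change paragraph expects both interventions to work through the sharing of positive experiences, and the Rationale sets this study apart from an earlier WhatsApp trial in Brazil because that trial did not test WhatsApp as a social network. The docu-drama session gives one hour to discussion and 2 × 15 = 30 minutes to viewing, and the tool 3 stem names the discussion. Asking about the presumed active ingredient is legitimate. This stands, and it is why sharing should stay in the guides as a probe. It does not make sharing the construct that the protocol defined.

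The definitions are also tied to questionnaires, while the focus groups have the wider task of finding what worked and what did not. That is fair, but the same section also has them assess the named constructs, and both guide titles name feasibility.

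Tool 5's lead-in frames the discussion as the acceptability and feasibility of WhatsApp for encouraging donation, and a good moderator can probe further. A narrower item under a broader lead-in is not a self-contradiction. Still, the scripted question is what each group is sure to hear.

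A reader might infer that the qualitative half of objective 3 answers a different question altogether, or that praise for sharing would be reported as evidence of effectiveness. The documents support neither. Items d–f, the barrier and improvement items and tool 3's message block address return donation or the intervention as a whole. The analysis uses verbatim transcripts and a framework with themes on barriers to and motivations for repeat donation, and return attempts are measured separately at Month 6.

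**Conclusion.** The point holds as a wording mismatch in two interview guides. Six scripted questions, three in each guide, rate the intervention on sharing experience. For four of them (acceptability and cultural appropriateness) this departs from the protocol's definition and the survey's object. For the other two (effectiveness) the plan supplies no definition. Neither guide asks directly how feasible the intervention was.

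The effect is that the focus-group findings on primary objective 3 are weaker than they need be and not fully comparable with the survey. Its size cannot be put in numbers, and it depends on how far moderators go beyond the script, which the documents do not settle. The primary outcome, sample size and quantitative analysis are not touched. Because the change alters what the focus groups measure and costs almost nothing, it should be made before the guides are used.

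**What to change.** 1. In tools 3 and 5, change the object in items a–c to the one used in the protocol and case report forms: *for promoting blood donation among first-time donors*. Keep sharing experiences as a probe under item g, where it already appears.
2. In item c, state that *effective* means encouraging first-time donors to return.
3. Add one parallel item to each guide: to what extent was it feasible to use WhatsApp (or the docu-drama) to promote donation among first-time donors?
4. In tool 5, delete the heading that assigns the guide to the docu-drama group, and replace the drama example in item b with *language of the messages and posts*.

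The cost is a minor re-approval of two guides. No participants, visits or staff are added.
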